#### **6.5.2.2. Protocol Deviations**

Protocol deviations will be compiled prior to database closure and will be summarized by category (n(%)) for the FA set by treatment arm. Categories will be assigned by the study Clinician.

#### **6.5.3. Study Treatment Exposure**

The following analyses will be based on the SA set.

##### **6.5.3.1. Exposure to Glasdegib**

The summary of treatment exposure for glasdegib will include the following information:

- Treatment duration (weeks);
- Cumulative dose (mg);
- Dose intensity (mg/day);
- Relative dose intensity (%).

The duration of glasdegib (in weeks) is defined as:

$$\text{Treatment duration (weeks)} = (\text{last dose date} - \text{first dose date} + 1)/7.$$

The cumulative dose (mg) of glasdegib is the sum of the actual dose levels that the patient received (ie, total dose administered (mg)).

The dose intensity (DI) and the relative dose intensity (RDI) of glasdegib will be calculated for each patient during the study. The DI (mg/day) of glasdegib during the study is defined as:

$$\text{DI (mg/day)} = [\text{cumulative dose (mg)}]/[\text{treatment duration (days) including any dose interruption period prior to permanent treatment discontinuation and excluding the HSCT period, if applicable}].$$

The RDI of glasdegib is defined as the ratio of the DI and planned dose intensity and expressed in %

$$\text{RDI (\%)} = 100 \times [\text{DI (mg/day)}/[100 \text{ (mg/day)}]].$$

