32. **PRO Collection during HSCT Post Remission Period (HSCT Period):** PRO will be completed on the day of conditioning regimen administration as described in Section 7.4, then on the day of stem cell infusion prior to infusion and any other clinical activities, then once a month after HSCT infusion (Day 0) until the subject-resumes glasdegib or placebo; then begin PRO assessments on Day 1 in SoA column labeled "Following Consolidation until up to 2 years post randomization). Optimally, subjects will complete electronic PROs (in tablet) themselves. However, if PRO tablets are not available to the subject during this HSCT period, subject if able, will complete the PRO over the phone with a study coordinator so the coordinator may complete the electronic tablet. The study coordinator will make no attempt to clarify, explain, interpret, influence or filter, but simply reading the questions verbatim and transcribing patient choice of answers directly onto the site tablet.

CCI

34. **HSCT-related information:** Donor details, type of transplant, day of donor stem cell infusion, and conditioning regimen (including radiation) will be collected in the CRF. Presence of GVHD prior to resuming glasdegib/placebo post HSCT will be reported in the CRF. HSCT-related information must be made available to the B1371019 study and must be able to be monitored. Post Remission HSCT period (**HSCT period**) is defined as time from start of conditioning until resuming glasdegib/placebo, death, withdrawal of consent, or entering follow up period post HSCT. No concomitant medications (including transfusions) will be collected during the HSCT period. Day 0 is defined as the day of stem cell infusion (HSCT). See Section 7.1.8.
35. **ANC engraftment:** ANC engraftment is defined as  $\geq 0.5 \times 10^9/L$  for 3 consecutive days without growth factor support. ANC engraftment must be documented prior to continuing glasdegib or placebo post-HSCT.

36. **SAE Collection post remission HSCT Period from HSCT (Day 0) until resumption of study therapy, death, or withdrawal:** All deaths regardless of causality, Grade 3 and Grade 4 treatment-related AEs, and SAE events that the investigator believes have at least a reasonable possibility of being related to study drug during the HSCT period are to be reported to the sponsor. Once subjects resume glasdegib or placebo following HSCT, events summarized in [Table 13](#) will be reported.

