### **Post Remission HSCT**

Subjects who are eligible for Post Remission HSCT will undergo HSCT per local standard of care. For HSCT, Day 0 is the first day of HSCT; this is the day when stem cells are infused.

For post remission HSCT, glasdegib or placebo will be interrupted at least 28 days before HSCT and resumed 30-60 days post date of stem cell infusion, once there is ANC engraftment, no  $\geq$  Grade 2 ongoing GVHD, and no ongoing SAEs that prevent resuming glasdegib/placebo in the judgement of the investigator. Confirmed ANC engraftment is defined by ANC  $\geq 0.5 \times 10^9/L$  for 3 consecutive days without growth factor support following HSCT using myeloablative or non-myeloablative conditioning regimen.

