#### HSCT Period

The HSCT period is defined as time from the start of the HSCT conditioning regimen until the subject re-starts glasdegib/placebo or cytarabine, death, post study follow-up, or withdrawal. Day 1 is the day of the HSCT. Note that in the Protocol this was referred to as Day 0 per common clinical practice. Per Protocol Section 8, there are limited data collection during the HSCT period beyond 28 days after the last investigational treatment administration prior to HSCT.

The cycle day for assessments occurring on or after the day of HSCT will be calculated as:

$$\text{Cycle day} = \text{Date of the assessment/event} - \text{date of HSCT} + 1.$$

The cycle day for HSCT conditioning regimen(s) will be negative as they occur prior to HSCT and calculated as:

$$\text{Cycle day} = \text{Date of the assessment/event} - \text{date of HSCT}.$$

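### Glasdegib relative dose intensity counts part of the protocol-required pre-transplant hold as missed dosing in patients who resume after HSCT

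*SAP*

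**What the plan says.** SAP Section 6.5.3.1 sets out the calculation for glasdegib:

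- Treatment duration runs from first dose date to last dose date, inclusive.
- On the numerator: "The cumulative dose (mg) of glasdegib is the sum of the actual dose levels that the patient received".
- Dose intensity (DI) divides that sum by treatment duration in days, with interruptions before permanent discontinuation left in and "excluding the HSCT period, if applicable".
- RDI is DI over a planned 100 mg/day, as a percentage.

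The excluded interval is defined in SAP Section 5.2.3: "The HSCT period is defined as time from the start of the HSCT conditioning regimen until the subject re-starts glasdegib/placebo or cytarabine", or until death, follow-up or withdrawal. The protocol starts it at the same point. In the Schedule of Activities (Table 1, footnote 34) the period "is defined as time from start of conditioning until resuming glasdegib/placebo, death, withdrawal of consent, or entering follow up period post HSCT". The non-intensive text in Protocol Section 5.5.1.3 also starts it at conditioning.

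The drug stops earlier than that. Under Post Remission HSCT in Protocol Section 5.5.1.2, "glasdegib or placebo will be interrupted at least 28 days before HSCT", with resumption 30 to 60 days after infusion if the stated conditions are met. The non-intensive study has the same hold.

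**The concern.** The hold and the exclusion start on different days. The hold starts at least 28 days before infusion; the exclusion starts at conditioning. Nothing in the SAP removes the days in between. If dosing later resumes, those days lie inside the first-to-last-dose span, contribute 0 mg to the numerator and count in full in the denominator. The patient has followed the protocol exactly and still shows a reduced RDI.

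RDI is usually read as a summary of how well a regimen was delivered and tolerated. Because the SAP already excludes the HSCT period, its authors evidently did not want transplant time to count against the drug. The exclusion simply starts too late to achieve that. A compliant patient could have no adverse event interruption under SAP Section 6.5.3.6 and yet an RDI well under 100%, with nothing in the exposure table to explain it.

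**Working it through.** The documents state no RDI value, so there is no figure of the plan's own to reproduce. The check applies the SAP formulas day by day to a fully compliant patient.

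**Inputs**

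- Dose: 100 mg on every permitted day (SAP 6.5.3.1 reference).
- Hold before infusion, H: 28 days, the protocol minimum.
- Resumption: Day 30 or Day 60 after infusion (Protocol 5.5.1.2).
- Days from start of conditioning to infusion, C: **an assumption**. The protocol leaves conditioning to local practice. The range shown is 4 to 14 days.
- Dosed days, D = days before the hold plus days after resumption: illustrative.

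**One case in full.** Take 60 dosed days, a 28-day hold, C = 7, resumption on Day 30 and 28 more dosed days.

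- Treatment duration = 60 + 28 + 30 + 28 = 146 days.
- HSCT period excluded = 7 + 30 = 37 days.
- Denominator = 146 − 37 = 109 days.
- Cumulative dose = 88 × 100 = 8,800 mg.
- DI = 8,800 / 109 = 80.7 mg/day, so RDI = 80.7%.
- Hold days left in the denominator = 28 − 7 = 21, and 88 + 21 = 109.

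With resumption on Day 60, duration is 176, the exclusion is 67 and the denominator is again 109. The resumption day cancels.

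**General form.** RDI = D / (D + H − C). With H = 28:

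| Dosed days D | C = 4 (24 days counted) | C = 7 (21 counted) | C = 14 (14 counted) |
|---|---|---|---|
| 88 (60 + 28) | 88/112 = 78.6% | 88/109 = 80.7% | 88/102 = 86.3% |
| 180 (90 + 90) | 180/204 = 88.2% | 180/201 = 89.6% | 180/194 = 92.8% |
| 270 (90 + 180) | 270/294 = 91.8% | 270/291 = 92.8% | 270/284 = 95.1% |
| 672 (100 + 572) | 672/696 = 96.6% | 672/693 = 97.0% | 672/686 = 98.0% |

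The last row is a full 2-year course with resumption on Day 30: 730 − 28 − 30 = 672 dosed days.

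**Boundaries**

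- RDI reaches 100% only if conditioning starts on the first hold day (C = 28).
- A hold longer than the minimum lowers it further: H = 42, C = 7, D = 270 gives 270/305 = 88.5%.
- A patient with 120 dosed days who never resumes has duration 120 and RDI 120/120 = 100%, because the last dose precedes the hold.
- If the exclusion starts on the first hold day, RDI is D/D = 100% in every case above.

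**The case against.** The best counter-argument is that the plan may already mean to exclude the hold. Protocol Section 5.5.5.1 exempts protocol-required interruptions from the 28-day discontinuation rule and gives the HSCT period as the example, which treats the hold as part of that period. This is good evidence of intent. It does not override the formal definitions in both documents, all of which start at conditioning, and a programmer working from SAP 5.2.3 would produce the lower number.

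The other objections limit the scope, and they stand:

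- **All transplanted patients.** A reader might infer that everyone who goes to HSCT is affected. The duration formula ends at the last dose, so only those who resume are. Resumption is restricted by engraftment, GVHD and SAE conditions, and SAP 3.2.1 bars it where MRD status cannot be determined. SAP Section 6 also expects few transplants in the non-intensive study.
- **All 28 hold days.** Days after conditioning starts are already excluded; only the earlier part counts.
- **Toxicity.** A reader might infer that the hold is reported as a toxicity interruption. SAP 6.5.3.6 counts an interruption as due to an AE only when the dosing CRF gives that reason.
- **Bias between arms.** The rule is the same in both arms, RDI is descriptive and no test is planned on it. Arm-level RDI would be distorted only if the share of patients resuming after HSCT differed, and the documents give no resumption rate.
- **China versus rest of world.** SAP Section 6 expects fewer transplants in China, which makes a regional distortion tempting to infer. The SAP defines China subset analysis sets but plans no RDI comparison between regions.

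**Conclusion.** The point holds for patients in either study who resume glasdegib/placebo after HSCT. As written, the SAP gives a fully compliant patient an RDI of about 79-86% with 88 dosed days, 92-95% with 270 and 97-98% over a full 2-year course, where the intended value is 100%. These figures rest on a 28-day hold and an assumed 4 to 14 days of conditioning before infusion. They describe single patients; no arm-level effect can be calculated from the documents.

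This is a minor point confined to the exposure summary. OS, type I error and the adverse event analyses are unchanged.

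**What to change.** In SAP Section 6.5.3.1, exclude from the DI and RDI denominator the protocol-required HSCT interruption, running from the first day of the pre-HSCT hold to the day before the first post-HSCT dose. Keep in the denominator any days interrupted for another recorded reason, such as an AE, before the hold began. The protocol sets a minimum for the hold but no maximum, so the SAP should say how the start of the hold is fixed when an earlier interruption runs straight into it. Otherwise the exclusion could absorb time lost to toxicity.

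Reconcile the meaning of HSCT period in SAP Sections 5.2.3 and 6.5.3.1 with its use in Protocol Section 5.5.5.1. Because the start at conditioning also governs concomitant medication collection (Protocol Section 5.8), a separately named interval for exposure would be the least disruptive way to do this. Treatment duration can stay as first to last dose.

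The cost is one SAP definition and its programming. Dosing and missed-dose dates, reasons for dose adjustment, and conditioning and infusion data are already recorded. No dosing rule changes.

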### **6.5.3.2. Exposure to Cytarabine (Induction, Intensive Study Only)**

The summary of treatment exposure for cytarabine in the induction cycles will include the following information:

- Treatment duration (weeks);
- Total number of infusions received;
- Cumulative dose (mg/m^2);
- Dose intensity (mg/m^2/day);
- Relative dose intensity (%).

Cytarabine is administered by intravenous (IV) infusion daily for 7 days, in 28 day cycles (5 days allowed in re-induction cycle).

The dose level for cytarabine captured on the CRF is calculated as actual dose administered/body surface area (BSA) (mg/m^2). The last available weight of the patient on or prior to the day of dosing will be used.

The duration of cytarabine (in weeks) during the study for a patient is defined as:

$$\text{Treatment duration (weeks)} = (\text{last dose date} - \text{first dose date} + 1)/7.$$

The cumulative dose (mg/m^2) of cytarabine per cycle is the sum of the actual dose levels that the patient received within that cycle (ie, total dose administered (mg)/BSA (m^2)). Cumulative dose (mg/m^2) of cytarabine is the sum of the actual dose levels that the patient received throughout induction.

Since the planned cytarabine dose may be 5 (Option 1: '5+2') or 7 (Option 2: '7+3') days in the re-induction cycle, the dose intensity (DI) and the relative dose intensity (RDI) of cytarabine will be calculated for each patient by cycle and across all cycles based on the actual treatment received. The DI (mg/m^2/day) of cytarabine is defined as:

$$\text{DI (mg/m}^2\text{/day)} = [\text{cumulative dose (mg/m}^2\text{)}]/[\text{number of days with a non-zero dose}].$$

The RDI of cytarabine is defined as the actual DI divided by the planned dose per day and expressed in %:

$$\text{RDI (\%)} = 100 \times [\text{DI (mg/m}^2\text{/day)}] / [100 \times (\text{mg/m}^2\text{/day)}].$$

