### **Cytarabine**

- Separate cytarabine dosing and schedules will be used for Induction and Consolidation per the local package insert (or SPC) or Investigational Product Manual (or SPC).
- **Induction 1:** Cytarabine will be administered (in parallel to daunorubicin) at a dose of 100 mg/m^2 daily by continuous IV infusion for 7 days (Days 1-7).
- **Induction 2,** if indicated based on ≥5% marrow blasts (or investigator judgment if <5% bone marrow blasts), The Investigator may choose either cytarabine 100 mg/m^2 IV daily on Days 1-5 or Days 1-7. Dose must be recalculated if the weight changes by >10%.

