### **Daunorubicin Dosing (Induction Only):**

- During **Induction 1**, daunorubicin 60 mg/m^2 daily IV on Days 1-3.

- **Induction 2**, if indicated based on  $\geq 5\%$  bone marrow blasts (or investigator judgment if  $< 5\%$  bone marrow blasts), the Investigator will choose either daunorubicin  $60 \text{ mg/m}^2$  IV daily on Days 1-2 or Days 1-3 with cytarabine. If clinical signs or symptoms of cardiac dysfunction are observed, multigated acquisition scan/echocardiogram (MUGA/ECHO) must demonstrate a LVEF  $\geq 45\%$  before initiation of Induction 2. Dose must be recalculated if the weight changes by  $> 10\%$ .
- If  $< 5\%$  bone marrow blasts: treatment with either or both of the following if a second Induction is not selected (per investigator judgment):
  - Consolidation with single-agent cytarabine  $3 \text{ g/m}^2$  IV for adults  $< 60$  years and  $1 \text{ g/m}^2$  for adults  $\geq 60$  years over 3 hours twice daily (BID) on Days 1, 3, and 5, every 28 days for up to 4 cycles or alternative single-agent cytarabine consolidation schedules may be used per local prescribing information.
  - HSCT per local standard of care.

A detailed dosing schedule is found in Table 7.

Table 7. Intensive Chemotherapy Doses and Dose Frequency: Glasdegib or Placebo in Combination with Daunorubicin and Cytarabine		
Days	Induction Therapy	
	Backbone Chemotherapya	Experimental Therapya,b,c
1-3	Administer Daunorubicin $60 \text{ mg/m}^2$ IV Administer cytarabine $100 \text{ mg/m}^2$ IV	Administer glasdegib $100 \text{ mg}$ PO or placebo PO
4-7	Administer cytarabine $100 \text{ mg/m}^2$ IV	
$\geq 8^d$		
Days	Second Induction if <math>\geq 5\%</math> bone marrow blasts or investigator judgement for <math>< 5\%</math> bone marrow blasts (Option 1: '5+2')	
	Backbone Chemotherapya	Experimental Therapya,b,c
1-2	Administer Daunorubicin $60 \text{ mg/m}^2$ IV Administer cytarabine $100 \text{ mg/m}^2$ IV	Administer glasdegib $100 \text{ mg}$ PO or placebo PO
3-5	Administer cytarabine $100 \text{ mg/m}^2$ IV	
$\geq 6^d$		
Days	Second Induction if <math>\geq 5\%</math> bone marrow blasts or investigator judgement for <math>< 5\%</math> bone marrow blasts (Option 2: '7+3')	
	Backbone Chemotherapya	Experimental Therapya,b,c

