#### **6.5.3.4. Exposure to Daunorubicin (Induction Only, Intensive Study Only)**

The summary of treatment exposure for daunorubicin will include the following information:

- Treatment duration (weeks);
- Total number of infusions received;
- Cumulative dose (mg/m^2);
- Dose intensity (mg/m^2/day);

- Relative dose intensity (%).

Daunorubicin is administered by intravenous (IV) infusion daily for 3 days, in 28 day cycles (2 days allowed in re-induction cycle).

The dose level for daunorubicin captured on the CRF is calculated as actual dose administered/BSA ( $\text{mg}/\text{m}^2$ ). The last available weight of the patient on or prior to the day of dosing will be used.

The duration of daunorubicin (in weeks) during the study for a patient is defined as:

$$\text{Treatment duration (weeks)} = (\text{last dose date} - \text{first dose date} + 1)/7.$$

The cumulative dose ( $\text{mg}/\text{m}^2$ ) of daunorubicin per cycle is the sum of the actual dose levels that the patient received within that cycle (ie, total dose administered ( $\text{mg}$ )/BSA ( $\text{m}^2$ )). Cumulative dose ( $\text{mg}/\text{m}^2$ ) of daunorubicin is the sum of the actual dose levels that the patient received throughout induction.

Since the planned daunorubicin dose is 2 (Option 1: ‘5+2’) or 3 (Option 2: ‘7+3’) days in the re-induction cycle, the DI and RDI of daunorubicin will be calculated for each patient by cycle and across all cycles based on the actual treatment received. The DI ( $\text{mg}/\text{m}^2/\text{day}$ ) of daunorubicin is defined as:

$$\text{DI (mg/m}^2/\text{day)} = [\text{cumulative dose (mg/m}^2\text{)}]/[\text{number of days with a non-zero dose}].$$

The RDI of daunorubicin is defined as the actual DI divided by the planned dose per day and expressed in %:

$$\text{RDI (\%)} = 100 \times [\text{DI (mg/ m}^2/\text{day)}]/[60 \times (\text{mg/m}^2/\text{day})].$$

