#### **6.5.3.5. Exposure to Azacitidine (Non-intensive Study Only)**

The summary of treatment exposure for azacitidine will include the following information:

- Treatment duration (weeks);
- Total number of injections/infusions received;
- Cumulative dose ( $\text{mg}/\text{m}^2$ );
- Dose intensity ( $\text{mg}/\text{m}^2/\text{day}$ );
- Relative dose intensity (%).

Azacitidine is administered by subcutaneous injection (SC) or intravenous (IV) infusion  $75 \text{ mg}/\text{m}^2$  daily for 7 days, in 28 day cycles.

The dose level for azacitidine captured in the CRF is calculated as actual dose administered/BSA ( $\text{mg}/\text{m}^2$ ). The last available weight of the patient on or prior to the day of dosing will be used.

The duration of azacitidine (in weeks) during the study for a patient is defined as:

$$\text{Treatment duration (weeks)} = (\text{last dose date} - \text{first dose date} + 1)/7.$$

The cumulative dose ( $\text{mg}/\text{m}^2$ ) of azacitidine per cycle is the sum of the actual dose levels that the patient received within that cycle (ie, total dose administered ( $\text{mg}$ )/BSA ( $\text{m}^2$ )).

Cumulative dose ( $\text{mg}/\text{m}^2$ ) of azacitidine is the sum of the actual dose levels that the patient received throughout the study.

The DI) and RDI of azacitidine will be calculated for each patient by cycle and across all cycles. The DI per day ( $\text{mg}/\text{m}^2/\text{day}$ ) of azacitidine is defined as:

$$\text{DI (mg}/\text{m}^2/\text{day}) = [\text{cumulative dose (mg}/\text{m}^2)]/[\text{7 days} \times \text{number of cycles with a non-zero dose}].$$

The RDI of azacitidine is defined as the actual DI divided by the planned dose per day and expressed in %:

$$\text{RDI (\%)} = 100 \times [\text{DI (mg}/\text{m}^2/\text{day})]/[75 (\text{mg}/\text{m}^2/\text{day})].$$

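### Induction RDI for cytarabine and daunorubicin averages over days dosed, so a wholly missed day cannot lower it, and the SAP's reason does not cover Induction 1

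*SAP*

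**What the plan says.** **Induction chemotherapy (intensive study).** SAP 6.5.3.2 divides cumulative cytarabine dose (mg/m²) by the "number of days with a non-zero dose" to obtain DI, and then: "The RDI of cytarabine is defined as the actual DI divided by the planned dose per day and expressed in" percent, with 100 mg/m²/day as the planned dose. SAP 6.5.3.4 repeats this for daunorubicin with 60 mg/m²/day: "The RDI of daunorubicin is defined as the actual DI divided by the planned dose per day and expressed in" percent. Both are computed for each cycle and over all cycles.

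**The reason given.** The SAP points to the variable planned length, 5 or 7 "days in the re-induction cycle, the dose intensity (DI) and the relative dose intensity (RDI) of cytarabine will be calculated" from what the patient actually received. For daunorubicin the lengths are 2 or 3 days.

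**Induction 1.** Protocol 5.5.1.2 fixes the first course: cytarabine "daily by continuous IV infusion for 7 days (Days 1-7") and daunorubicin "daily IV on Days 1-3". The SAP sections restate these lengths and allow the shorter ones only in re-induction.

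**The other drugs.** SAP 6.5.3.5 defines azacitidine RDI in the same sentence, "The RDI of azacitidine is defined as the actual DI divided by the planned dose per day and expressed in" percent, but its DI divides by 7 days times the "number of cycles with a non-zero dose". SAP 6.5.3.1 divides cumulative glasdegib dose by treatment duration with interruptions counted in and the HSCT period taken out.

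**The concern.** A reader normally takes RDI as the share of planned treatment that was delivered. Under the induction formula an omitted full-dose day leaves the numerator and the denominator together, so the ratio does not move. The line therefore reports dose reductions and is blind to omitted days. It can also rank a patient who received less drug above one who received more.

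Within the intensive study, the glasdegib RDI falls for interruptions while the chemotherapy RDI does not. Across the two studies, one defining sentence yields two different quantities. At stake is how an exposure table is read, in particular whether near-100% induction RDI is taken to mean that the backbone was delivered as planned.

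**Working it through.** The SAP states no RDI value, so there is no figure to reproduce. The check applies its formulas to dosing patterns assumed for illustration; the documents do not say how often such patterns occur.

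**Inputs.** Planned daily dose: cytarabine 100, daunorubicin 60, azacitidine 75 mg/m² (SAP 6.5.3.2, 6.5.3.4, 6.5.3.5). Planned Induction 1 days: 7 and 3 (Protocol 5.5.1.2). Planned Induction 1 totals: 7 × 100 = 700 mg/m² and 3 × 60 = 180 mg/m².

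**Formulas.**
- SAP induction RDI = 100 × (cumulative dose / days dosed) / planned daily dose.
- SAP azacitidine RDI = 100 × (cumulative dose / (7 × cycles dosed)) / 75.
- Planned-total RDI = 100 × cumulative dose / planned total.

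**Induction 1.**

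| Pattern | SAP RDI | Planned-total RDI |
|---|---|---|
| Cytarabine, 3 of 7 full-dose days | (300/3)/100 = 100% | 300/700 = 42.9% |
| Cytarabine, 7 half-dose days | (350/7)/100 = 50% | 350/700 = 50.0% |
| Daunorubicin, 1 of 3 full-dose days | (60/1)/60 = 100% | 60/180 = 33.3% |
| Daunorubicin, 2 of 3 full-dose days | (120/2)/60 = 100% | 120/180 = 66.7% |

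The SAP formula returns 100% for any 1 to 7 full-dose cytarabine days and any 1 to 3 full-dose daunorubicin days. The first two rows show the ranking problem: 300 mg/m² reads 100%, 350 mg/m² reads 50%.

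**Induction 2 and across cycles.** A complete '5+2' course is 100% of its own plan, but would read 500/700 = 71.4% and 120/180 = 66.7% against '7+3'. A second induction stopped after 3 full-dose cytarabine days reads 100% under the SAP; it is 300/500 = 60.0% of '5+2' or 300/700 = 42.9% of '7+3'. Four cytarabine days in Induction 1 plus a complete 5-day re-induction give (900/9)/100 = 100% under the SAP and 900/1200 = 75.0% of plan. Here the planned total depends on the option chosen.

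**Azacitidine, same defining sentence.**
- 3 of 7 full-dose days in one cycle: 225/7 = 32.14 mg/m²/day; 32.14/75 = 42.9%. Days missed within a dosed cycle count.
- One full cycle given and one skipped: 525/(7 × 1) = 75 mg/m²/day; 75/75 = 100%. Wholly skipped cycles do not count.

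**The case against.** **The formula is disclosed, reasoned and does what it says.** This stands in part. Nothing in the SAP is miscalculated: RDI is defined as DI over the planned daily dose, and the printed formula gives that. A reader might infer an arithmetic error; the documents do not support one. The variable-length reason is also sound for Induction 2 and reaches the across-cycle figure, which pools a fixed course with a variable one. It does not reach the by-cycle Induction 1 figure.

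**Azacitidine RDI is no clean standard.** This stands. It ignores skipped cycles and can misorder patients too: one full-dose cycle (525 mg/m²) gives 525/7/75 = 100%, while six half-dose cycles (1575 mg/m²) give 1575/42/75 = 50%. It would be wrong to infer that azacitidine RDI captures all missed treatment. The contrast holds only for days missed within a dosed cycle.

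**Nobody plans to compare the two studies' RDI lines.** Correct: SAP section 4 keeps the populations separate, and each formula is printed under its own drug. The mismatch with glasdegib, however, sits inside the intensive study.

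**Missed doses show elsewhere.** This stands and is the main reason the point is small. SAP 6.5.3.2 and 6.5.3.4 also report treatment duration, infusion counts and cumulative dose. SAP 6.5.3.6 counts interruptions due to AEs, defined as 0 mg doses. SAP 6.6.1 tabulates AEs leading to interruption or withdrawal by drug, and SAP 6.5.2.1 gives discontinuation of each drug by reason. The 6.5.3.6 and 6.6.1 outputs cover AE-related events only. A reader might infer that omitted infusions would vanish from the report; they would not. They are absent only from the RDI line.

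**Conclusion.** The point holds as a minor one about definition and labelling. The induction RDI for cytarabine and daunorubicin cannot fall for a wholly missed day, and for by-cycle Induction 1 the SAP gives no reason that applies. In the assumed patterns the gap is 100% against 42.9% (cytarabine, 3 of 7 days) or 33.3% (daunorubicin, 1 of 3 days); the real size depends on how often infusions are omitted, which the documents do not indicate.

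No effect on efficacy conclusions should be inferred. The summary is descriptive, is made in the safety analysis set, uses the same formula in both arms, and feeds no test or decision rule. The change is optional but worth making, because Induction 1 can be corrected with totals that follow directly from the protocol.

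**What to change.** **Induction 1 (by cycle).** Report RDI = 100 × cumulative dose / 700 mg/m² for cytarabine and / 180 mg/m² for daunorubicin. The per-cycle cumulative dose is already derived, so this changes one denominator.

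**Induction 2 and across cycles.** If the selected option is recorded, divide by its planned total (cytarabine 500 or 700 mg/m², daunorubicin 120 or 180 mg/m²), adding the Induction 1 total for the across-cycle figure. If it is not recorded, keep the present formula and label the line *mean daily dose on days given, % of planned daily dose*. The documents do not say whether the option is captured. SAP 6.5.3.3 says that the intended dose is not captured for consolidation and drops RDI there, so the CRF should be checked first.

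**Cost.** A short SAP wording change and minor programming; where only the label changes, almost nothing. No data collection, dose or schedule is affected.
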